3.2.6. Summary of Anticipated Benefits and Risks

The combination of lenalidomide with SC administration of daratumumab is anticipated to have a positive benefit-risk profile when used for maintenance treatment of patients with newly diagnosed multiple myeloma who are MRD positive and anti-CD38 antibody naïve. Please refer to Section 3.2.1 for additional information. This assessment is based on the following:

• Strategies directed at improving and/or maintaining depth of response are needed to improve clinical outcomes for patients with newly diagnosed multiple myeloma.

- The addition of daratumumab to the standard of care lenalidomide, which is the current a standard of care regimen for maintenance treatment in patients with newly diagnosed multiple myeloma, may improve long-term outcomes through improvement in MRD conversion rate.
- Given the potential advantages of SC administration of daratumumab (refer to Section 3.2.2.2 for detailed information), including shorter time of administration, fewer injection-related reactions, and comparable clinical response rates when compared with administration of daratumumab via IV infusion, the SC route of administration will be used in this study.
- The assessment of primary endpoint of MRD negativity at 12 months post-maintenance will be conducted using a sensitive NGS (sensitivity cutoff of 10⁻⁵) assay (Adaptive Biotechnologies' NGS-based MRD assay), thus providing valuable data on the depth of response achieved with the combination of daratumumab and lenalidomide maintenance treatment in newly diagnosed multiple myeloma patients.
- We expect that the benefits of addition of SC daratumumab to lenalidomide, as maintenance treatment, will outweigh the risks, even among patients who may achieve a CR or better after transplant. As discussed in Section 3.2.1, prolonged administration of daratumumab in conjunction with lenalidomide does not result in an increased total risk of AEs based on data from ongoing trials.
- The potential risks for the study will be mitigated by monitoring via the Independent Data Monitoring Committee and the sponsor's medical monitor during the conduct of the study.

In summary, there is a strong rationale for evaluating SC daratumumab in combination with lenalidomide as maintenance treatment for patients with newly diagnosed multiple myeloma who are anti-CD38 naïve and MRD positive after frontline ASCT.

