4.1. Inclusion Criteria

Each potential patient must satisfy all of the following criteria to be enrolled in the study. Each patient:

- 1. Must be 18 to 79 years of age.
- 1. Must have newly diagnosed multiple myeloma with a history of a minimum of 4 cycles of induction therapy, have received HDT and ASCT within 12 months of the start of induction therapy, and be within 6 months of ASCT on the date of randomization.
- 2. Must have a VGPR or better response assessed per IMWG 2016 criteria at the time of randomization.
- 3. Must have archived bone marrow samples collected before induction treatment (ie, at diagnosis) or before transplant (eg, at the end of induction) or have existing results on the

index MM clone based on Adaptive Biotechnologies' NGS-based MRD assay. Archived bone marrow samples will be used for calibration of myeloma clonal cells to facilitate assessment of the primary end point by NGS. If an existing result on index myeloma clone is available from Adaptive Biotechnologies' NGS-based MRD assay, as part of institutional procedures, an archived bone marrow sample is not required as long as Adaptive Biotechnologies is able to retrieve historical results on the index myeloma clone form the clinical database. Any one of the following archived samples are required:

- a. Greater than 1 mL viable frozen bone marrow aspirated aliquot (preferred) collected in an EDTA tube, frozen, and stored at a temperature of -80°C, or
- b. Non-decalcified diagnostic bone marrow aspirate clot sections (block or slides) for MRD assessment:
- An FFPE block of bone marrow aspirate clot, or slides (preferably 5, if available),
 5 μm each, of non-decalcified bone marrow, or
- ii. Slides (preferably 5, if available), bone marrow aspirate smear,
- iii. Please note, bone marrow core sections are not acceptable samples for analysis.
- iv. In exceptional circumstances when index myeloma clone cannot be identified from the archived bone marrow sample, a post-transplant sample can be used to identify myeloma clone with permission from the Sponsor.

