11.1. Patient Information

The primary and secondary efficacy analysis will be performed based on the intent-to-treat population, which will include all randomized patients.

Safety will be evaluated for the safety population, which includes all treated patients who receive at least 1 dose of randomized therapy. Subgroup analyses will be performed as appropriate, and details will be specified in the SAP.

Continuous variables will be summarized using descriptive statistics such as mean, standard deviation, and range. Categorical variables will be summarized using frequency tables. For time-to-event variables, the Kaplan-Meier method will be used for descriptive summaries.

The primary analysis will be conducted at 2-sided alpha level of 0.05.

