Response rates by IMWG 2016 criteria including CR or better rate and sCR rate, defined as the proportion of subjects who achieve the respective responses prior to the first subsequent antimyeloma therapy per computer algorithm in accordance with the IMWG criteria, during or after the study treatment. All subjects are assumed to be VGPR at baseline to enter the study per inclusion criteria. Subgroup analysis will be performed for CR or better rate per computer algorithm with forest plot provided. In addition, responses per investigator assessment by IMWG 2016 criteria will be summarized. Shift tables will be provided to summarize the best responses from baseline vs. post-baseline for each treatment group.

Duration of CR, calculated from the date of initial documentation of a response of CR or sCR at or after randomization to the date of first documented evidence of PD (as defined in the IMWG criteria), or death due to PD, whichever occurs first, for subjects who have CR or better as their best response. Subjects who have not progressed or who die due to causes other than disease progression will be censored at the last disease evaluation before the start of subsequent antimyeloma therapy. Subjects who achieved CR or sCR prior to randomization will use randomization date as their starting time of CR or sCR for calculating duration of CR.

Time to the first response of CR or better is defined as the time between randomization and the first efficacy evaluation at which the subjects meet all criteria for CR or better based on computerized algorithm, according to IMWG response criteria. For subjects who achieved CR or sCR prior to randomization, time to CR or better will be set as 0 day.

In addition to protocol specified other secondary efficacy endpoints, progression-free survival on next line of therapy (PFS2) and time to subsequent therapy will be evaluated.

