5.4.2. Analysis Methods

The analysis of the overall MRD (10^{-5}) conversion rate at any time after randomization, durable MRD negativity rate, the CR or better rate, and sCR rate will be performed similarly to that for the primary endpoint on the FAS, as described in Section 5.2.3. Similarly, for thresholds 10^{-4} and 10^{-6} , the overall MRD negativity rate at any time after randomization will be analyzed similarly as for the threshold 10^{-5} .

The time-to-event variables (ie., OS, duration of CR, PFS2 and time to subsequent antimyeloma therapy) will be performed using the approach for PFS, as described in Section 5.3.2.

Time to the first response of CR or better will be summarized using descriptive statistics for those who reached CR or better response.

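### Time to CR or better mixes 0-day entries for patients already in CR with real conversion times, in responders only, so the arm that converts more patients will tend to look slower unless it also converts markedly faster

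*SAP*

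**What the plan says.** SAP 5.4.1 sets the clock: "Time to the first response of CR or better is defined as the time between randomization and the first efficacy evaluation" at which all criteria for CR or better are met by the computer algorithm. It adds a rule for patients already there: "For subjects who achieved CR or sCR prior to randomization, time to CR or better will be set as 0 day".

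SAP 5.4.2 gives the method: "Time to the first response of CR or better will be summarized using descriptive statistics for those who reached CR or better response". OS, duration of CR, PFS2 and time to subsequent therapy are handled like PFS; time to CR is not in that list.

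Patients in CR can enter. Protocol 4.1 states: "Must have a VGPR or better response assessed per IMWG 2016 criteria at the time of randomization". Protocol 3.2.6 expects benefit to outweigh risk "even among patients who may achieve a CR or better after transplant".

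Two other statements in SAP 5.4.1 bear on this. One is "All subjects are assumed to be VGPR at baseline to enter the study per inclusion criteria". The other is "Shift tables will be provided to summarize the best responses from baseline vs. post-baseline for each treatment group".

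**The concern.** The 0-day entries describe patients before any study drug. The positive times describe what happens on study treatment. Patients who never reach CR are left out. One summary of this mixture does not measure how fast treatment produces CR.

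The mixture also has a direction. If the share already in CR is about the same in both arms, extra conversions in one arm add positive times to that arm and thin out its zeros. Its mean rises, and often its median too. A better conversion rate can then be read as slower response. At stake is the reading of one descriptive table, not the trial's main conclusions.

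The sentence treating all subjects as VGPR at baseline also sits badly with a rule written for subjects in CR or sCR before randomization. Read literally, it would leave the 0-day rule with nobody to apply to.

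**Working it through.** The documents state no figure for time to CR, no share in CR at entry and no conversion rates, so there is no plan figure to reproduce. All rates below are assumptions.

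**Inputs**
- From the documents: 107 patients per arm (SAP 1.4). Response visits after C1D1 are at C3, C6, C9, C12, C18, C24, C30 and C36 (Protocol Time and Event Schedule, Part 1). With 28-day cycles these fall at about 1.8, 4.6, 7.4, 10.1, 15.6, 21.2, 26.7 and 32.2 months.
- Assumed: among converters, 20%, 20%, 15%, 15%, 12%, 8%, 6% and 4% first reach CR at those visits, the same in both arms (mean m = 10.37 months, median 7.4). Conversion rate c among patients not in CR at entry is 30% (R) and 60% (DR). The share b in CR at entry is equal in both arms and is varied.

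**Formula.** The planned responder-only mean is

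mean = (1 − b)·c·m / [b + (1 − b)·c] = m × {1 − b / [b + (1 − b)·c]}

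For b > 0 and fixed m, this rises strictly with c. For b = 0 it equals m whatever c is.

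**Worked case, b = 30%**
- R: converters 0.70 × 0.30 = 0.21; responders 0.30 + 0.21 = 0.51; zeros 0.30/0.51 = 59%; mean 0.21 × 10.37/0.51 = 4.27 months. More than half are zeros, so the median is 0.
- DR: converters 0.70 × 0.60 = 0.42; responders 0.72; zeros 0.30/0.72 = 42%; mean 0.42 × 10.37/0.72 = 6.05 months. Zeros plus the C3 converters are 42% + 0.20 × 58% = 53%, so the median is 1.8 months.

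**Range over b** (R vs DR, months). The break-even ratio is the DR/R ratio of converters' mean times below which the mean reverses.

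| b | Mean | Median | Break-even ratio |
|---|---|---|---|
| 0% | 10.37 vs 10.37 | 7.4 vs 7.4 | 1.00 |
| 10% | 7.57 vs 8.75 | 4.6 vs 7.4 | 0.86 |
| 20% | 5.65 vs 7.32 | 1.8 vs 4.6 | 0.77 |
| 30% | 4.27 vs 6.05 | 0 vs 1.8 | 0.71 |
| 40% | 3.22 vs 4.91 | 0 vs 0 | 0.66 |
| 50% | 2.39 vs 3.89 | 0 vs 0 | 0.62 |

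At b = 30% the break-even is (0.21/0.51)/(0.42/0.72) = 0.71. If DR converters take 0.8 of R's mean time, DR still shows the longer mean (4.27 vs 4.84). At 0.7 the order flips narrowly (4.27 vs 4.23).

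**Smaller treatment difference.** With b = 30% and conversion 50% vs 60%, the means are 5.58 vs 6.05, the medians both 1.8, and the break-even 0.92.

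**Chance variation.** In 5,000 simulated trials of 107 per arm (b = 30%, conversion 30% vs 60%, equal converter timing), DR had the longer mean in 90%. It had the longer median in 88%, with 11% tied.

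**The proposed estimate on the same assumptions.** Take patients not in CR at entry, keep non-converters, and ignore PD and death for simplicity. By the C12 visit 70% of converters have converted, so cumulative CR is 0.30 × 0.70 = 21% (R) and 0.60 × 0.70 = 42% (DR). Median time to CR is not reached in R and is 21.2 months in DR. The arm that converts more now reads as the better arm.

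**The case against.** **The direction is conditional.** A reader might infer that a more effective DR arm is bound to be reported as slower. The documents do not support that: they give no baseline CR share, CR rates or conversion times, and the illustration assumes equal converter speed. The effect vanishes at b = 0, the mean reverses if DR converts markedly faster, and the median can be 0 in both arms. Randomization is stratified by cytogenetic risk, not baseline response, so the zeros balance only in expectation. At b = 30% the standard error of the between-arm difference in share is √(2 × 0.30 × 0.70/107) = 6.3 points. All of this stands, so the point is a tendency.

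**No protocol breach.** A reader might also infer that the SAP departs from Protocol 11.1, which says that for time-to-event variables "the Kaplan-Meier method will be used for descriptive summaries". That is not established. Time to CR is not among the protocol's endpoints (Table 1), Protocol 11 leaves details to the SAP, and SAP 5.4.2 keeps time to CR out of its time-to-event list. No protocol-specified analysis is changed.

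**Other outputs help.** The CR-or-better rate is analysed on the full analysis set with non-responders included, and the shift tables set baseline against best response by arm. Provided they use actual baseline response, these let a careful reader see how many patients entered in CR and how many converted. That too stands, but neither output shows timing among patients who entered without CR.

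**Conclusion.** The concern holds as a low-severity point. The two SAP rules together make time to CR uninterpretable as a measure of speed. With similar non-zero baseline CR shares, the arm that converts more patients will tend to show the longer mean, and often the longer median, unless it also converts markedly faster.

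On the assumed rates with 10% to 50% in CR at entry, the gap in means is about 1.2 to 1.8 months (8.75 − 7.57 = 1.18; 6.05 − 4.27 = 1.78). It shrinks to about 0.5 month (6.05 − 5.58 = 0.47) when conversion is 50% versus 60% at 30% in CR at entry. These sizes depend on the assumed entry share, conversion rates and converter timing; the algebraic direction needs only b > 0, equal b and equal converter speed.

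SAP 5.1.1 makes all efficacy endpoints other than the primary and PFS exploratory, and no test of time to CR is planned. The primary endpoint and PFS are unaffected.

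**What to change.** In SAP 5.4.1 and 5.4.2:

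1. Remove the 0-day rule.
2. Define the analysis population as full-analysis-set subjects not in CR or sCR at randomization, including those who never reach CR.
3. Estimate cumulative incidence of first CR or better by arm, with PD and death as competing events and censoring at the last disease evaluation before subsequent therapy. Ordinary Kaplan-Meier that censors PD and death is not an equivalent substitute.
4. Report by arm the number already in CR or sCR at randomization.
5. Reconcile the sentence that assumes VGPR for everyone at baseline with the handling of patients who entered in CR, for example by saying whether it means at least VGPR, and confirm that the shift tables use actual baseline response.

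The cost is SAP wording and a small programming change on data already collected. The population is smaller: with 30% in CR at entry, about 0.70 × 107 = 75 patients per arm would remain.

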- Screening Phase: Screening is to be conducted within 60 days prior to randomization; randomization must be within 6 months of the transplant date. Patients must have undergone HDT and ASCT within 12 months of the start of induction therapy. Tandem transplants are not allowed.
- Maintenance Phase: Comprised of up to thirty-six, 28-day cycles. Patients are to receive study treatment (ie, daratumumab in combination with lenalidomide or lenalidomide alone), until confirmed PD, unacceptable toxicity, or the end of study treatment.
 - Note: PD based on 1 of the laboratory tests alone must be confirmed by at least 1 repeat investigation performed at least 1 day later. Clinical judgment should prevail; however, repeat assessments within 3 weeks can be used as a general guideline.
- EOT Visit: An EOT visit is to be scheduled 30 days (± 7 days) after the last dose of study treatment(s) or, if a patient begins new therapy for the treatment of multiple myeloma, as soon as possible prior to the start of next-line therapy.

In this study, in accordance with the IMWG 2016 criteria consensus recommendations, a line of subsequent therapy is defined as one or more cycles of a planned treatment program. A new line of therapy starts when a planned course of therapy is modified to include other treatment agents (alone or in combination) because of PD, relapse, or toxicity.

- Follow-up Phase: After the EOT visit, patients will continue to be followed until the end of the study. The end of the study is defined as 36 months from the date of randomization of the last patient. If a patient has died, the date and cause of death will be collected and documented in the eCRF.
 - After confirmed PD or the start of a new treatment for multiple myeloma, patients will be contacted by telephone for follow-up information on secondary primary
 malignancy, next-line therapy, date of PD on next-line therapy, and/or survival (all patients). Written documentation of information obtained via telephone call must be
 available for review in source documents.

	STUDY PHASES/VISITS ^a				
Procedure	SCREENING	Maintenance (Cycles 1 – 36)	ЕОТ	FOLLOW-UP (FROM THE DATE OF LAST STUDY TREATMENT UNTIL THE END OF STUDY)	Notes

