Assessment of lytic bone disease	х	As clinically indicated to document response or progression.	x	-	• The same methodology used during screening should be used throughout the study for comparison purposes
Extramedullary soft tissue plasmacytomas (in patients with history of extramedullary soft tissue plasmacytoma, physical or radiologic examination to be done as applicable)	x	As applicable, by physical exam every 4 weeks, or by radiologic exam every 12 weeks; to be conducted within 14 days before a scheduled visit.	-	-	 Not required during screening if performed as part of standard of care within 30 days before screening.
Other malignancy (other primary or recurrent malignancy diagnosed after initiation of study treatment)	-	x	x	Every 6 months	Data on other malignancy, survival status, date of PD on next line of therapy, next line of therapy along with start/stop date should be entered in eCRF at each study visit, as applicable, during the maintenance treatment and, every 6 months (24 weeks) during follow- up phase.
Next-line therapy and start/stop date	-	Х	Х		-
Survival	-	Х	X		-
Date of PD on next-line therapy	-	Х	X		-
ONGOING PATIENT REVIEW					
Adverse events	Continuous	from the time of signing of the days) after last dose of	Note: If a patient is unable to return to the site for the EOT Visit, then he/she should be contacted to collect adverse events and		

	STUDY PHASES/VISITS ^a					
PROCEDURE	Screening	Maintenance (Cycles 1 – 36)	ЕОТ	Follow-up (from the date of last study treatment until the end of study)	Notes	
Concomitant medications					concomitant therapies that occur within 30 days (± 7 days) after the last dose of study treatment(s).	
					See Section 8 and Section 11.1 for detailed instructions regarding concomitant medication use and reporting adverse events, respectively.	
Key: β -hCG = beta hormone human chorion	nic gonadotropi	n; ALT = alanine aminotransf	erase; an	tiHBc = antibody to hepatitis B core	e antigen; antiHBs = antibody to hepatitis B surface	
antigen; ASCT = autologous stem cell	transplant; AS	T = aspartate aminotransferase	; BUN =	blood urea nitrogen; C = cycle (cycl	le number); COPD = chronic obstructive pulmonary	
disease; CR = complete response; CT	= computed tor	nography; D = day (day numb	er of cyc	le); ECG = electrocardiogram; ECO	G = Eastern Cooperative Oncology Group; eCRF =	

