PFS2 is defined as the time from randomization to progression on next line of therapy or death, whichever comes first. Disease progression on the next line of treatment will be based on investigator assessment. Any deaths are considered as PFS2 events. Subjects who start next line of therapy without disease progression on study treatment will be censored at the last disease assessment before starting next line of therapy. For subjects who start next line of therapy after progression on study treatment, are still alive and not yet progress on next line of therapy or progressed on or after a 2nd line of next therapy, they will be censored on minimum of the last date of follow-up and start date of 2nd line of next therapy minus 1. Subjects without any post-baseline follow-up will be censored at the randomization. Time to subsequent antimyeloma therapy is defined as the time from randomization to the start of subsequent antimyeloma treatment. Death due to PD without start of subsequent therapy will be considered as event. Subjects who withdrew consent to study or are lost to follow, or die due to causes other than disease progression will be censored at the date of death or the last date known to be alive.

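### The PFS2 rules conflict for subjects who start next-line therapy without progression: a later death is both an event and censored, and a later next-line progression is never counted

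*SAP*

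**What the plan says.** PFS2 is not a protocol endpoint; SAP 5.4.1 adds it. Four sentences there matter.

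- Definition: "PFS2 is defined as the time from randomization to progression on next line of therapy or death, whichever comes first".
- Deaths: "Any deaths are considered as PFS2 events".
- Next line started without progression: "Subjects who start next line of therapy without disease progression on study treatment will be censored at the last disease assessment" before that line begins.
- Next line started after progression: the censoring is limited to subjects who "are still alive and not yet progress on next line of therapy or progressed on or after a 2nd line of next therapy". They are censored at the earlier of last follow-up and the day before a second next line.

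SAP 5.4.2 analyses PFS2 with the PFS methods of 5.3.2. SAP 5.1.1 makes it exploratory, tested at two-sided 0.05 without multiplicity adjustment.

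The protocol collects the data needed. In the Time and Event Schedule, Part 1, footnote a, the follow-up phase provides: "After confirmed PD or the start of a new treatment for multiple myeloma, patients will be contacted by telephone for follow-up information", and the items include "next-line therapy, date of PD on next-line therapy, and/or survival (all patients"). The notes column of the same schedule requires eCRF entry of "Data on other malignancy, survival status, date of PD on next line of therapy, next line of therapy along with start/stop date", every 6 months during follow-up.

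**The concern.** The definition does not require progression on study treatment to come first, and the death sentence has no exception. The sentence on early switchers then censors all of them before the new therapy, whatever happens afterwards. Two programmers could each follow the text and build different PFS2 datasets.

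What is at stake is the meaning of the PFS2 hazard ratio. PFS2 asks how patients fare through the next line. Subjects who leave study treatment early, for example for intolerance, are unlikely to be a random subset, and treatment is open-label. If they are censored at the switch, their outcome on the next line drops out, and for them PFS2 does no more than PFS, which SAP Table 4 already censors at that point.

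**Working it through.** The plan gives no sample size, event count or power for PFS2, so there is no stated figure to reproduce. The check is to run the SAP 5.4.1 sentences over each patient path under both possible orders of precedence.

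| Path | Death sentence prevails | Censoring sentence prevails |
|---|---|---|
| Next line without PD, no next-line PD, dies | Event at death | Censored before next line |
| Next line without PD, next-line PD, alive | Censored before next line | Censored before next line |
| Next line without PD, next-line PD, then dies | Event at the later death date | Censored before next line |
| Next line without PD, no next-line PD, alive | Censored before next line | Censored before next line |
| PD, next line, next-line PD | Event at next-line PD | Event at next-line PD |
| PD, next line, dies | Event at death | Event at death |
| No next line, dies | Event at death | Event at death |

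Row 1 is the contradiction. Rows 2 and 3 show that a next-line progression after an early switch is never counted as the event, whichever sentence prevails. The last three rows agree, so the defect is confined to early switchers.

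**Can the group exist?** Protocol Section 8.4 does not permit other anti-myeloma therapy before PD is confirmed. But footnote a of the Time and Event Schedule, Part 1, lists toxicity among the reasons for a new line, and SAP Table 4 lists subsequent therapy before progression or death as a reason for censoring PFS.

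**Size, by illustration only.** From the plan: 107 per arm, accrual over 1 year, median PFS 60 and 120 months, study end 36 months after the last randomization (so 36 to 48 months of follow-up). Assumed, not in the documents:

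- exponential times;
- a constant rate of switching without PD, equal in both arms, up to 36 × 28 / 30.4375 = 33.1 months;
- a median of 24 months from next-line start to progression or death;
- the censoring sentence prevails.

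| Assumed switching per year | Early switchers of 214 | PFS2 events kept | PFS2 events discarded | Share discarded |
|---|---|---|---|---|
| 0% (Section 8.4 fully followed) | 0 | all | 0 | 0% |
| 0.5% | about 2.5 | about 28 | about 1.3 | 1.3 / 29.5 = 4% |
| 1% | about 5 | about 28 | about 2.6 | 2.6 / 30.8 = 8% |
| 2% | about 10 | about 28 | about 5 | 16% |
| 4% | about 20 | about 27 | about 10 | 27% |
| 6% | about 29 | about 26 | about 15 | 36% to 37% |

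A second set of assumptions (5% to 15% of each arm assigned to switch, uniformly over months 1 to 24) gives a loss of about 3 to 8 events per arm. If the death sentence prevails instead, the loss is smaller: only next-line progressions go uncounted, and those followed by death return as later events.

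**The case against.** **The death sentence may be about cause.** In the same section, duration of CR and time to subsequent therapy count only deaths due to PD. On that reading, the PFS2 death sentence says that cause is irrelevant, and the next sentence says when follow-up stops. This is plausible. But the sentence on switches after PD is limited to living subjects and the disputed one is not, so the text stays ambiguous. A reader might infer that deaths after an early switch are certainly lost; the documents support only that their handling is unsettled. This reading does nothing for the lost next-line progressions.

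**The group may be very small.** Under Section 8.4 a switch before confirmed PD is a protocol departure. This stands. A reader might take the upper rows of the illustration as an expected loss of a quarter or more of the events. The documents give no switching rate, and zero is within the range.

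**Bias between arms is not shown.** A reader might infer a distorted treatment comparison. With equal switching at 2% to 6% per year, the simulated PFS2 hazard ratio is about 0.51 to 0.54 under the censoring rule, against 0.52 to 0.53 with no switching; counting post-switch events moves it to about 0.57 to 0.67. That is a difference in what is estimated, not a demonstrated bias. Differential switching is possible, but no document gives a basis for quantifying it.

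**PFS2 keeps its main purpose.** A reader might conclude that the rule leaves PFS2 with nothing beyond PFS. That holds only for early switchers; subjects who progress and then start a next line are still followed to next-line progression or death.

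**Other endpoints capture part of this.** Deaths after an early switch remain OS events, and the switch itself enters time to subsequent therapy. This is true, but neither supplies the next-line progression.

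**Conclusion.** SAP 5.4.1 is internally inconsistent for subjects who start next-line therapy without progression on study treatment. Two findings follow from the text without any assumption: the handling of a later death has two contrary answers and no stated precedence, and a later progression on that line, which meets the PFS2 definition and is collected, is never counted. The SAP's optional analysis that does not censor at subsequent therapy (5.3.2) is written for PFS and does not settle this.

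The size cannot be derived from the documents. It ranges from nothing, if Section 8.4 is followed throughout, to the figures illustrated above, which rest on assumed switching rates, an assumed next-line median and the censoring sentence prevailing. Because PFS2 is exploratory and outside the testing hierarchy, neither the primary endpoint nor PFS is affected. The point is worth correcting because a hazard ratio and p-value for PFS2 will be produced and the correction is cheap.

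**What to change.** In SAP 5.4.1, delete the sentence that censors subjects who start next-line therapy without progression. Replace it with wording to this effect: *Progression on the first subsequent line, or death from any cause, is a PFS2 event whether or not progression on study treatment came first. Subjects who start a next line and are alive without such an event are censored at the earlier of last follow-up and the day before the start of the second next line.*

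The second sentence extends the existing rule for switches after PD to everyone who starts a next line. Censoring early switchers simply at last follow-up would treat the two groups differently once a second next line begins.

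The current rule may be kept as a sensitivity analysis, provided the SAP states how deaths after an early switch are handled in it.

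Cost: SAP wording and one derivation, with no new data collection. The downside is that PFS2 will then include outcomes after early switches, so the number of early switchers should be reported by arm beside it.
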